8.1.4 Monitoring

The Investigator/institution must agree to the inspection of study-related records by the regulatory authority/Apexigen (or designee) representative and must allow direct access to source documents to the regulatory authority/Apexigen (or designee) representative/IRB/IEC. Apexigen (or designee) representative will review onsite study records and directly compare them with source documents, discuss the conduct of the study with the Investigator, and verify that the facilities remain acceptable.

The Investigator must notify Apexigen (or designee) promptly of any inspections by regulatory authorities and forward promptly copies of inspection reports to Apexigen (or designee).

8.1.5 Confidentiality

All records identifying the subject will be kept confidential to the full extent of the law.

Subject names will not be supplied to the sponsor. Only the subject number will be recorded on the eCRF. If the subject name appears on any other document (e.g., pathologist report) or study materials (e.g., biopsy tissue slides), then that information must be redacted before a copy of the document is supplied to Apexigen (or designee). Study data stored on a computer will be stored in accordance with local data protection laws and regulations. Subjects will be informed in writing that representatives of the sponsor, IRB/IEC, or regulatory authorities may inspect their medical records to verify the information collected, and all personal information made available for inspection will be handled in strictest confidence and in accordance with local data protection laws and regulations.

If the results of the study are published, the subject's identity will remain confidential.

The Investigator will maintain a list to enable subjects' records to be identified in accordance with applicable laws and regulations and according to the terms and agreed upon in such subjects' signed consent forms.

8.1.6 Investigational Site Training

Study personnel involved in conducting this study will be qualified by education, training, and experience to perform their respective task(s).

This study will not use the services of study personnel where sanctions have been invoked or where there has been scientific misconduct or fraud (e.g., loss of medical licensure or debarment).

Systems with procedures that assure the quality of every aspect of the study will be implemented.

If necessary, Apexigen (or designee) will provide investigational staff training prior to study initiation. Training topics will include, but are not limited to, GCP, AE reporting, study details and procedure, study documentation, informed consent, and enrollment of WOCBP.

8.2 Data Collection and Handling

8.2.1 Case Report Forms

As part of the responsibilities assumed by participating in the study, the Investigator agrees to maintain adequate case histories for the subjects treated as part of the research under this protocol. The Investigator agrees to maintain accurate eCRFs and source documentation as part of the case histories. These source documents may include subject diaries, laboratory reports, and other documents. Apexigen (or designee) will supply the eCRF, which will be completed in English.

Data collection will involve the use of the EDC system, to which only authorized personnel will have access.

The Investigator or designee must enter all results collected during the clinical study into eCRFs. Guidelines for completion of eCRFs will be reviewed with study site personnel at the site initiation visits. Investigators are responsible for approval of the entered/corrected data. Detailed instructions may be found in the other study-specific documents.

All entries made on the eCRF must be verifiable against source documents. In addition to periodic monitoring occurring within the system by study monitors, programmatic edit checks and data listings will be used to review the data for completeness, logic, and adherence to study protocol. As a result of this monitoring and these checks and queries may be electronically issued to the clinical study sites and electronically resolved by those sites.

All data collected in the context of this study will be stored and evaluated per regulatory requirements and applicable guidance for electronic records. Also, data will be stored and evaluated in such a way as to assure subject confidentiality in accordance with the legal and regulatory requirements applying to protected health information. Study records (e.g., copies of eCRFs and regulatory documents) will be retained at the study site, along with adequate source documentation. The study file and all source data should be retained for the time period required by applicable regulatory requirements and will not be destroyed until written notification is given by Apexigen (or designee) for destruction.

8.3 Publications

The data collected during this study are confidential and proprietary to Apexigen. Any publications or abstracts arising from this study require approval by Apexigen prior to publication or presentation and must adhere to Apexigen's publication requirements (as set forth in the approved clinical trial agreement). All draft publications, including abstracts or detailed

summaries of any proposed presentations, must be submitted to the sponsor at the earliest practicable time for review, but at any event not less than 30 days before submission. Apexigen shall have the right to delete any confidential or proprietary information contained in any proposed presentation or abstract and may delay publication for up to 60 days for purposes of filing a patent application.

9. List of Abbreviations

Abbreviation	Definition
ADA	Anti-drug antibodies
ADCP	Antibody-dependent cellular phagocytosis
AE	Adverse event
ALT	Alanine aminotransferase
ANC	Absolute neutrophil count
APC	Antigen-presenting cell
aPTT	Activated partial thromboplastin time
AR	Adverse reaction
AST	Aspartate aminotransferase
AUC _{0-∞}	Area under the curve extrapolated to infinity
AUC _{0-t}	Area under the curve at the last measurable time point
BCR	B-cell receptor
BRAF	Human proto-oncogene encoding B-Raf protein
CD40	Cluster of differentiation 40
CD40L	CD40 ligand
C _{max}	Maximum serum concentration
CNS	Central nervous system
CR	Complete response
CTLA-4	Cytotoxic T-lymphocyte associated protein 4
DCs	Dendritic cells
DOR	Duration of response
DL	Dose level
DLT	Dose-limiting toxicity
ECG	Electrocardiogram
ECOG	Eastern Cooperative Oncology Group
eCRF	Electronic case report form
EDC	Electronic data capture
EOT	End of treatment
FDA	Food and Drug Administration
GCP	Good Clinical Practice
GLP	Good Laboratory Practice
HIV	Human immunodeficiency virus
ICF	Informed consent form
ICH	International Conference on Harmonisation
IEC	Independent Ethics Committee
Ig	Immunoglobulin
IL	Interleukin
IND	Investigational New Drug application
INR	International normalized ratio

Abbreviation	Definition
inNSCLC	Immunotherapy naïve NSCLC
IRB	Institutional Review Board
iRECIST	Immune-related RECIST Modified RECIST 1.1 for Immune-based Therapeutics
ISR	IND safety report
IV	Intravenous
K _d	Dissociation constant
mAb	Monoclonal antibody
mL	Milliliter
MTD	Maximum tolerated dose
MM	Unresectable or metastatic melanoma
NCI-CTCAE	National Cancer Institute-Common Terminology Criteria for Adverse Events

APPENDIX A: Eastern Cooperative Oncology Group Performance Scale

Grade	Description
0	Normal activity, fully active, able to carry on all pre-disease performance without restriction
1	Symptoms, but fully ambulatory, restricted in physically strenuous but ambulatory and able to carry out work of a light or sedentary nature (e.g., light housework, office work)
2	Ambulatory and capable of all self-care but unable to carry out any work activities. Up and about more than 50% of waking hours
3	Capable of only limited self-care, confined to bed or chair more than 50% of waking hours
4	Completely disabled. Cannot carry on any self-care. Totally confined to bed or chair
5	Death

1. LIST OF ABBREVIATIONS

1.1 Abbreviations

Abbreviation	Description
ADA	Anti-drug antibodies
ADCP	Antibody-dependent cellular phagocytosis
AE	Adverse event
ALT	Alanine aminotransferase
ANC	Absolute neutrophil count
APC	Antigen-presenting cell
aPTT	Activated partial thromboplastin time
AR	Adverse reaction
AST	Aspartate aminotransferase
AUC_{0-∞}	Area under the curve extrapolated to infinity
AUC_{0-t}	Area under the curve at the last measurable time point
BCR	B-cell receptor
BOR	Best overall response
BRAF	Human proto-oncogene encoding B-Raf protein
CD40	Cluster of differentiation 40
CD40L	CD40 ligand
C_{max}	Maximum serum concentration
CNS	Central nervous system
CR	Complete response
CTLA-4	Cytotoxic T-lymphocyte associated protein 4
DCs	Dendritic cells
DoR	Duration of response
DL	Dose level
DLT	Dose-limiting toxicity
ECG	Electrocardiogram
ECOG	Eastern Cooperative Oncology Group
eCRF	Electronic case report form
EDC	Electronic data capture
EOT	End of treatment
FDA	Food and Drug Administration
GCP	Good Clinical Practice
GLP	Good Laboratory Practice
HIV	Human immunodeficiency virus
ICF	Informed consent form
ICH	International Conference on Harmonisation
IEC	Independent Ethics Committee
Ig	Immunoglobulin
IL	Interleukin
IND	Investigational New Drug application

Abbreviation	Description
INR	International normalized ratio
inNSCLC	Immunotherapy naïve NSCLC
IRB	Institutional Review Board
iRECIST	Immune-related RECIST Modified RECIST 1.1 for Immune-based Therapeutics
ISR	IND safety report
IV	Intravenous
Kd	Dissociation constant
mAb	Monoclonal antibody
mL	Milliliter
MTD	Maximum tolerated dose
MM	Unresectable or metastatic melanoma
NCI-CTCAE	National Cancer Institute-Common Terminology Criteria for Adverse Events
NOAEL	No observed adverse effect level
NSCLC	Non-small cell lung cancer
ORR	Overall response rate
PBMC	Peripheral blood mononuclear cells
PD	Progressive disease/disease progression
PD-1	Programmed death receptor-1
PD-L1	Programmed death-ligand 1
PD1-MM	MM with progressive disease during treatment with anti-PD-1/PD-L1
PDn	Pharmacodynamics
PK	Pharmacokinetics
PFS	Progression-free survival
PFSR	Progression-free survival rate
PR	Partial response
PT	Prothrombin time
PTT	Partial thromboplastin time
RCC	Advanced renal cell carcinoma
RECIST	Response Evaluation Criteria in Solid Tumors
RP2D	Recommended Phase 2 dose
SAE	Serious adverse event
SAR	Suspected adverse reaction
SSAR	Serious suspected adverse reaction
TCR	T-cell receptor
TKI	Tyrosine kinase inhibitor
T_{max}	Time to maximum serum concentration
TNFR	Tumor necrosis factor receptor
ULN	Upper limit of normal
WOCBP	Women of childbearing potential

2. INTRODUCTION

2.1 Background & Rationale

Among the promising approaches to activating therapeutic anti-tumor immunity is the modulation of host immune system. Immune modulation includes inhibitory or stimulatory pathways in the immune system that are crucial for activating the immune response, maintaining self-tolerance, and modulating the duration and amplitude of physiological immune responses. Modulation of immune checkpoints by antibodies against immune inhibitory molecules has shown clinical benefits for patients with various solid tumors such as melanoma, lung cancer, bladder cancer, renal cell carcinoma [1, 2, 3]. Currently, both antagonistic monoclonal antibodies (mAb) against immune inhibitory molecules such as cytotoxic T-lymphocyte associated protein 4 (CTLA-4) and programmed death receptor-1 (PD-1)/ programmed death-ligand 1 (PD-L1) and agonistic antibodies against immune costimulatory molecules such as CD40 and OX40 are under active development for different cancer indications and is believed that combination of such immunomodulatory agents could lead to a cure for cancer [4].

Apexigen has developed the mAb APX005M, which binds and activates CD40, a costimulatory molecule expressed by antigen presenting cells (APC). As such, APX005M is a CD40 agonistic antibody. The cell surface molecule CD40, a member of the tumor necrosis factor receptor (TNFR) superfamily, plays an important role in induction of tumor apoptosis and regulation of immune activation, especially in crosstalk between T cells and APCs [5]. CD40 is expressed by dendritic cells (DC), B cells, monocytes, and some non-lymphoid cells [6]. The natural ligand (CD40L) for CD40 is CD154, which is expressed on activated T cells and provides a major component of T cell “help” for immune response. Agonistic CD40 antibodies can substitute for the function of CD154 on T cells to boost immunity. Signaling through CD40 on APCs, including dendritic cells (DCs), monocytes, and B cells, can, in turn, enhance the T cell response via improvement in antigen processing and presentation and through the release of cytokines from activated APCs [7, 8][7, 8]. Therefore, an agonistic CD40 antibody can activate and stimulate both innate and adaptive immunity.

CD40 is also expressed on many tumor cells and can mediate a direct cytotoxic effect. In addition to B cell lymphoma, CD40 expression has been reported in 30–70% of primary human solid tumor samples including melanoma and carcinomas [9]. Activation of CD40 on tumor cells results in tumor cell apoptosis and inhibition of tumor growth [10]. Due to its action on both immune and tumor cells, CD40 has been studied as a target for novel cancer immunotherapy; agonistic anti-CD40 antibodies have been demonstrated to be potent stimulators of tumor immune responses in both animal models and cancer patients [11, 12, 13, 14].

The potential mechanisms of action for an agonistic anti-CD40 antibody, depending on its isotype, include stimulation of immune response by activating antigen processing and presentation, recruitment of immune effectors such as natural killer (NK) cells and macrophages, and direct cytotoxic effects on tumor cells. Thus, the desired therapeutic CD40 agonist antibody should have these functionalities.

2.2 Study Objectives and Analyses

This statistical analysis plan describes the methods and statistical models to be applied for the generation of the statistical report. As a reference, the Amendment 4 of the protocol (dated on 10 October 2019) has been used in order to prepare this document.

2.2.1 Primary Objective

- Determine the maximum tolerated dose (MTD) and the recommended Phase 2 dose (RP2D) of APX005M when given in combination with nivolumab (Phase 1b only)
- Evaluate the overall response rate (ORR) by RECIST v1.1 in each cohort/group (Phase 2 only)

2.2.2 Secondary Objectives

- Evaluate safety of the APX005M and nivolumab combination by analysing the incidence and severity of AEs and specific laboratory abnormalities graded according to NCI-CTCAE, v4.03
- Evaluate the 6-month progression-free survival (PFS) rate (PFSR) in each cohort/group (Phase 2 only)
- Evaluate duration of response (DoR) in each cohort/group by RECIST v1.1 (Phase 2 only)
- Evaluate the median PFS by cohort/group by RECIST v1.1 (Phase 2 only)

2.2.3 Exploratory Objectives

- Determine the immune PDn of the APX005M and nivolumab combination
- Determine the PK of APX005M
- Assess incidence of APX005M ADA
- Identify blood and/or tumor biomarkers that correlate with efficacy and/or resistance
- Evaluate the ORR in each cohort/group by immune related RECIST (iRECIST)
- Evaluate DoR and median PFS in each cohort/group by iRECIST

Note: Pivotal will not be responsible for TLFs using data from the correlative laboratory samples. The current SAP will not include the analyses about the following endpoints: PK, ADA, association between PDn markers and PK, and association between biomarkers and anti-tumor activity. These analyses will be carried out by Apexigen, Inc. or a different provider.

2.2.4 Additional exploratory efficacy analyses (Phase 2 only)

Exploratory analyses of efficacy will be carried out including occurrences of unconfirmed responses:

- ORR - including unconfirmed response (efficacy and safety population)
- DoR - including unconfirmed response (efficacy and safety population)

Exploratory analysis: Characterization of progressive disease. (efficacy population)

2.2.5 Subgroup efficacy analyses (Phase 2 only)

Subgroup analyses by prior therapy:

- Subgroup analysis Cohort 1: Prior therapy - platinum-based vs other
- Subgroup analysis Cohort 1: Prior therapy - anti-EGFRi+TKI vs other

- Subgroup analysis Cohort 2: Prior therapy - pembrolizumab vs. nivolumab
- Subgroup analysis Cohort 2: Prior therapy - BRAF/MEK inhibition vs other
- Subgroup analysis Cohorts 3A+3B: Prior therapy - pembrolizumab vs. nivolumab

Subgroup analysis by LDH

- Subgroup analysis Cohort 2: LDH baseline values above the upper normal range vs normal/lower

Subgroup analysis by country

- Subgroup Analysis by country: US vs. non-US

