			
• Add supportive care guidelines for myocarditis toxicity• Add definition of correlative laboratory testing• Specify that the dose modification regarding neutropenia related to Grade 3-4 and not Grades 2 to 4• Remove summary of changes appendices as red-line tracked changes versions of the amendment will be provided.• Remove summary of changes appendices as redline versions will be provided.
--	--	--	--

Synopsis

Protocol Title		
A Study to Evaluate the Safety and Efficacy of the CD40 Agonistic Antibody APX005M Administered in Combination with Nivolumab in Subjects with Non-small Cell Lung Cancer and Subjects with Metastatic Melanoma		
Investigational Products		

• APX005M (humanized IgG1κ mAb that binds CD40)• Nivolumab (fully human IgG4κ mAb that blocks the interaction between PD-1 and its ligands, PD-L1 and PD-L2)		
Sponsor Apexigen, Inc.	Protocol Number APX005M-002	Phase of Development Phase 1b-2
Objectives		
Primary: Phase 1b: 
• Determine the MTD and the RP2D of APX005M when given in combination with nivolumab Phase 2: 
• Evaluate the ORR by RECIST 1.1 in each cohort/group		
Secondary: 
• Evaluate safety of the APX005M and nivolumab combination• Evaluate the 6-month progression-free survival (PFS) rate (PFSR) in each cohort/group• Evaluate the DOR and median PFS in each cohort/group by RECIST 1.1		
Exploratory: 
• Determine the immune PDn of the APX005M and nivolumab combination• Determine the PK of APX005M• Assess incidence of APX005M ADA• Identify blood and/or tumor biomarkers that correlate with efficacy and/or resistance• Evaluate the ORR by immune related RECIST (iRECIST) in each cohort/group• Evaluate DOR and median PFS in each cohort/group by iRECIST		
Study Period		
Date first subject enrolled (US): 5/17/2017 Date first subject enrolled (EU): 3/1/2019		

Estimated date last subject enrolled: 5/15/2020

Study Design

This is a phase 1b-2 study. Adult subjects with non-small cell lung cancer and subjects with metastatic melanoma will be enrolled. The study will include 2 parts.

Study Phase	Dose Level	APX005M		Nivolumab		
		mg/kg		mg		N
Phase 1b Dose-escalation	DL 1	0.03	q 21 days	360	q 21 days	3
	DL 2	0.1	q 21 days	360	q 21 days	3
	DL2a	0.2	q 21 days	360	q 21 days	3 to 6

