2.3 Study Design

This is a Phase 1b-2 study. The study will include 2 parts.

Phase 1b dose-escalation of APX005M:

[figure not shown]
- Up to 4 dose levels of APX005M administered IV every 21 days
- In combination with nivolumab 360 mg IV every 21 days
- Participants with inNSCLC or PD1-MM

Phase 2 dose-expansion (Simon optimal 2-stage design):

- The RP2D dose of APX005M administered IV every 21 days in combination with nivolumab 360 mg IV
- 3 cohorts
 - Cohort 1: Participants with inNSCLC
 - Cohort 2: Participants with PD1-MM
 - Cohort 3: Participants with PD1-NSCLC
 - Group A: Participants with PD1-NSCLC with best response of progressive disease or with stable disease < 16 weeks while on previous PD-1/PD-L1 containing regimen
 - Group B: Participants with PD1-NSCLC with tumor response or with stable disease ≥ 16 weeks while on previous PD-1/PD-L1 containing regimen

Participants will be evaluated for tumor response approximately every 8 weeks following the first dose of investigational product. An ORR of at least 22% (6 out of 24 response evaluable participants) in the inNSCLC cohort and 5% (1 out of 12 response evaluable participants) in the PD1-MM cohort or PD1-NSCLC (Group A or B) is required in Stage 1 for that cohort to proceed to Stage 2. Enrollment may continue into Stage 2 while the planned number of participants for Stage 1 are followed for efficacy.

Figure 1 APX005M-002 Study Design

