2.3.2 Eligibility Criteria

2.3.2.1 Phase-Specific Criteria

Phase 1b: Participants that meet eligibility criteria for Phase 2 Cohorts 1 or 2 and all the general eligibility criteria.

Phase 2 Cohort 1: Histologically or cytologically confirmed, immunotherapy naïve, metastatic or locally advanced non-small cell lung cancer not amenable to curative treatment. Participants may be treatment naïve or could have received one prior platinum-based chemotherapy for non-small cell lung cancer for any indication (adjuvant, part of combined modality therapy or for metastatic disease) within the past 3 years. Participants with no or unknown activating mutation (e.g., EGFR, ALK, ROS) are eligible for this study. Participants with a documented activating mutation (e.g., EGFR, ALK, ROS) amenable to tyrosine kinase inhibitor therapy, must also have received the appropriate therapy and progressed.

Phase 2 Cohort 2: Participants with histologically or cytologically confirmed unresectable or metastatic melanoma that had confirmed progressive disease during treatment with anti-PD-1/PD-L1 therapy. Participants with BRAF wild type or unknown status must have received only anti-PD-1/PD-L1 therapy. Participants with BRAF activating mutation could have also received a BRAF inhibitor and/or MEK inhibitor regimen prior to anti-PD-1/PD-L1 therapy.

Confirmed PD during treatment with anti-PD-1/PD-L1 therapy should be documented by 2 consecutive tumor assessments at least 4 weeks apart (the second scan may be used as the baseline scan for this study if it was performed within the 21 days prior Cycle 1 Day 1). Participants should start study treatment no later than 8 weeks following the last dose of anti-PD-1/PD-L1 therapy.

Participants with ocular melanoma are excluded.

Phase 2 Cohort 3: Participants with histologically or cytologically confirmed, metastatic or locally advanced NSCLC not amenable to curative treatment. Participants must have disease progression on an immediately preceding PD-1/PD-L1 containing regimen. Participants could have received no more than one platinum containing regimen, or if participants have a documented activating mutation (e.g. EGFR, ALK, ROS) amenable to tyrosine kinase inhibitor therapy, must also have received the appropriate therapy and progressed before the PD-1/PD-L1 containing regimen.

Based on response to previous PD-1/PD-L1 containing regimen, participants will be enrolled in one of the following groups:

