- Group A: Participants with best response of progressive disease or with stable disease < 16 weeks
- Group B: Participants with tumor response or with stable disease ≥16 weeks.

If possible, confirmed PD during treatment with anti-PD-1/PD-L1 therapy should be documented by 2 consecutive tumor assessments at least 4 weeks apart (the second scan may be used as the baseline scan for this study if it was performed within the 21 days prior Cycle 1 Day 1). Participants should start study treatment no later than 8 weeks following the last dose of anti-PD-1/PD-L1 containing regimen.

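### The pembrolizumab-versus-nivolumab subgroup pools Cohort 3 Groups A and B without stratification, so it can be confounded by the A:B mix if that mix and the true response rates both differ

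*SAP*

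**What the plan says.** SAP 2.2.5 lists the Phase 2 subgroup efficacy analyses. The prior-therapy and LDH lines for Cohorts 1 and 2 each stay inside one cohort. The Cohort 3 line does not: "Subgroup analysis Cohorts 3A+3B: Prior therapy - pembrolizumab vs. nivolumab". It names no endpoint, stratification, adjustment or test, and SAP 5.4.2 gives no subgroup method.

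SAP 2.3.2.1 sets the group by earlier outcome: "Based on response to previous PD-1/PD-L1 containing regimen, participants will be enrolled in one of the following groups". SAP 2.3 defines Group A as "best response of progressive disease or with stable disease < 16 weeks while on previous PD-1/PD-L1 containing regimen" and Group B as "tumor response or with stable disease ≥ 16 weeks while on previous PD-1/PD-L1 containing regimen".

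SAP 5.1 gives each group its own two-stage design: stop at 0 responses in 12, otherwise continue to 37 and reject the null at 4 or more. P0 is 5% and P1 is 20% in both groups. SAP 5.4.2 estimates ORR, DoR and PFS separately for each cohort/group. Neither document says how prior pembrolizumab and prior nivolumab are expected to divide between A and B.

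**The concern.** The factor pooled over is itself an outcome of the therapy being compared. Group membership records how the patient fared on the earlier PD-1/PD-L1 containing regimen, and the subgroup then asks whether the choice of earlier drug matters. If patients of one drug sit more often in Group B, and Group B responds better to the study combination, the pooled contrast credits the drug with a difference that belongs to the group. With the mix reversed, it could hide a real drug difference.

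The A:B ratio in the pool is also not a natural one. It follows from the group targets and from stopping within each group, so it can be near 37:37, 12:37 or 37:12. Enrolment may run on during Stage 1 follow-up, so a stopped group can also end above 12.

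What is at stake is the reading of one secondary table, not a primary or secondary endpoint.

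**Working it through.** **The plan's own figures.** For Group A or B (SAP 5.1), an exact binomial calculation of the rule 0/12 then 3/37 gives a type I error of 0.0935 at 5%, power of 0.9024 at 20%, and a probability of early stopping of 0.95^12 = 0.540 at 5%. A search returns the same optimal design, so the stated design reproduces. The SAP gives no figure for the subgroup itself.

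**Size of the false gap.** Suppose there is no drug effect inside either group. Let f_P and f_N be the fractions of the pembrolizumab and nivolumab patients who are in Group B, and let p_A and p_B be the true ORRs. Then:

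false gap = (f_P − f_N) × (p_B − p_A)

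It is zero if either bracket is zero.

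**Assumed inputs, none of them in the documents.** ORR is 5% in A and 20% in B, which borrows the planning P0 and P1. Everyone in Cohort 3 had one of the two drugs. The shares on prior pembrolizumab are as shown.

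**Both groups reach 37.** For shares of 30% in A and 70% in B:
- pembrolizumab: 0.3 × 5% + 0.7 × 20% = 15.5%
- nivolumab: 0.7 × 5% + 0.3 × 20% = 9.5%
- gap: 0.4 × 15 = 6.0 points

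For 20%/80%, the rates are 17.0% and 8.0%, a gap of 0.6 × 15 = 9.0 points. In whole patients, with 7 A and 30 B on pembrolizumab and 30 A and 7 B on nivolumab, they are 6.35/37 = 17.2% and 2.9/37 = 7.8%.

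Whole-patient results, with the exact chance of observing a gap of 10 points or more in favour of pembrolizumab:

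| Share in A / B | Pembrolizumab | Nivolumab | Gap (points) | Chance of observing ≥10 points |
|---|---|---|---|---|
| 50% / 50% | 12.5% | 12.5% | 0 | 9% |
| 40% / 60% | 13.9% | 11.1% | 2.8 | 19% |
| 30% / 70% | 15.5% | 9.5% | 6.1 | 32% |
| 20% / 80% | 17.2% | 7.8% | 9.3 | 49% |

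With a common ORR in both groups (both 5% or both 20%), the expected gap is 0 in every row.

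**Group A has 12 and B has 37, 20%/80% mix.** Pembrolizumab has 2 A and 30 B, nivolumab 10 A and 7 B. The expected rates are (2 × 0.05 + 30 × 0.20)/32 = 19.1% and (10 × 0.05 + 7 × 0.20)/17 = 11.2%, a gap of 7.9 points. These use A's true rate. If A stopped because of 0/12, its observed rate is 0. With B left at 20%, the figures become 6.0/32 = 18.8% and 1.4/17 = 8.2%, a gap of 10.5 points.

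**After the change.** Within a group, or stratified by group, the expected false difference is 0 at every mix. The cost is precision. At 20%/80% with 37 each:
- The smaller cell in each group has 7 patients. An observed 0/7 has an upper 90% Clopper-Pearson limit of 1 − 0.05^(1/7) = 35%.
- The Mantel-Haenszel weights are equal (7 × 30/37 in each group). The variance of the stratified difference is (1/7 + 1/30) × (0.0475 + 0.16)/4 = 0.00914, a standard error of 9.6 points.
- The variance of the pooled difference is [(7 × 0.0475 + 30 × 0.16) + (30 × 0.0475 + 7 × 0.16)]/37² = 0.00561, a standard error of 7.5 points.

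**The case against.** The strongest answer is that nothing in the documents shows an imbalance. They give no split of prior drug by group, and they plan both groups with the same P0 and P1; under equal ORRs the false gap vanishes. This stands against any claim that the comparison *is* confounded, which a reader might infer from the group definitions alone. It does not remove the risk. P0 and P1 are decision thresholds, not a statement that the true rates are equal, and separate rules allow one group to succeed while the other fails.

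Second, the subgroup carries no test and no decision rule, and A and B are reported separately in the main analysis, so a reader can see whether they differ. That limits the harm. The main tables are not, however, planned to show how prior drug divides between the groups, and that is the other half of the condition.

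Third, stratifying on prior response is not clean confounder adjustment, because prior response is partly a result of the prior drug and that drug was not randomised. The cells would also be small. Both points stand: a stratified figure removes the effect of the A:B mix but does not isolate a causal effect of the prior drug.

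Fourth, the table shells are in an external file not available here (SAP 7) and may already show 3A and 3B in separate columns. If so, only the SAP line needs to say it.

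**Conclusion.** The point holds as a conditional one. The pooled Cohort 3 contrast can show a prior-drug difference with no such effect inside either group. In the main 37:37 illustration the expected false gap runs from 0 to about 9 points. That rests on the assumed ORRs of 5% and 20% and the assumed shares; it is zero if either the mix or the ORR is the same. Unequal stopping does not remove it. The separate Simon decisions and the per-group estimates are unaffected.

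Three stronger readings are not supported:
- **That the contrast would steer the choice of population for later development.** No passage links the subgroup to any such decision.
- **That the groups are defined by response to pembrolizumab or nivolumab as such.** They are defined by response to a PD-1/PD-L1 containing regimen, which may include other agents.
- **That "Subgroup Analysis by country: US vs. non-US" has the same fault.** SAP 5.4 offers an overall Phase 2 summary only where nothing else is specified. SAP 4.2 and 5.4.2 specify PFS and DoR by cohort, and ORR, DoR and PFS by cohort/group. The later EU start alone does not show that the cohort mix differs by country. At most that line lacks detail.

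**What to change.** In SAP 2.2.5, replace the combined Cohort 3 line with the prior pembrolizumab-versus-nivolumab subgroup shown within 3A and within 3B, and add a table of group counts by prior drug. If a combined figure is wanted, stratify it by group: a Mantel-Haenszel difference for ORR, and Kaplan-Meier curves by prior drug within each group for the time-to-event endpoints. Label all of it descriptive, and state that prior response is an outcome of the earlier regimen and that prior drug was not randomised. Bring the external table shells into line.

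The cost is SAP wording and shells. Data collection, sample size and decision rules do not change. The separate columns may contain cells as small as 7 participants with wide intervals. A stratified estimate can still draw on both groups, at the loss of precision shown in the working.
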